6.5.3. Clinical Laboratory Assessments

Clinical laboratory assessments for safety monitoring will be performed by an accredited local laboratory. Blood and urine samples for hematology, serum chemistry and urinalysis, will be prepared using standard procedures.

PSA sample will be collected at Screening (unless performed within one month of enrollment and results are available), and results will be entered into the eCRF.

The following laboratory tests will be performed at Screening, Day 1 (after the administration of the IP), Day 7, and Day 28:

- Hematology: White blood cell (WBC) count with differential, red blood cell (RBC) count, Hb, hematocrit, platelet count, mean corpuscular volume (MCV).
- Blood chemistry profile: albumin, alkaline phosphatase (AP), alanine transaminase (ALAT), aspartate transaminase (ASAT), blood urea nitrogen (BUN), corrected calcium, chloride, creatinine, eGFR (preferably CKD-EPI), glucose, uric acid, gamma-glutamyl transpeptidase (GGT), lactate dehydrogenase (LDH), potassium, sodium, total bilirubin and total protein.
- Urinalysis: (dipstick), appearance, color, pH, specific gravity, protein, glucose and occult blood, RBC and WBC counts, Casts per low power field (Casts/lpf), Protein (dipstick test accepted).

Table 2 summarizes general laboratory assessments to be performed.

Hematology	Blood Chemistry	Urinalysis [*]
• WBC with differential	• BUN	• Appearance
• RBC	• Serum creatinine	• Color
• Platelets	• eGFR	• pH
• Hb	• Albumin	• Specific gravity
• MCV	• Total bilirubin	• Glucose
• Hematocrit	• AP	• Occult blood
• PSA (Screening visit only)	• AST/ASAT	• RBC/hpf
	• ALT/ALAT	• WBC/hpf
	• Gamma-GT	• Casts/lpf
	• Sodium	• Protein (dipstick test accepted)
	• Potassium	
	• Chloride	
	• LDH	
	Corrected Calcium	
	• Glucose	
	• Total protein	
	• Uric acid	

 Table 2
 Summary of Laboratory Assessments

*A urine sample will be collected at each visit and analyzed at the clinical site if dipstick results are abnormal. WBC = white blood cell; RBC = red blood cell; Hb = hemoglobin; MCV = mean corpuscular volume; PSA = prostate specific antigen; BUN = blood urea nitrogen; eGFR = estimated glomerular filtration rate; AST/ASAT = aspartate aminotransferase; ALT/ALAT = alanine aminotransferase; gamma-GT = gamma glutamyl transferase; LDH = lactate dehydrogenase; pH = potential of hydrogen; hpf = high power field; lpf = low power field.

The total volume of blood required per patient for clinical laboratory assessment will be approximately 70 mL (approximately 15 mL on each sampling at Screening, Day 7, and Day 28), and approximately 25 mL on Day 1. Blood and urine samples will be analyzed in an accredited local laboratory.

6.5.4. Imaging assessments

6.5.4.1. Imaging Procedure During the Phase 1 Portion of the Study

⁶⁸Ga-PSMA-R2 PET/CT imaging (four scans) will be performed using a standard integrated PET/CT system. Patients will be placed on the scanner table to allow a vertex to mid-thigh low-dose CT scan without contrast (used for anatomic localization and attenuation correction), followed immediately by emission scan after ⁶⁸Ga-PSMA-R2 injection. PET scans will be performed from vertex to mid-thigh in 3D (3-dimentional acquisition) mode. Please refer to Section 6.5.4.2 for more details.

Maximum standardized uptake values (SUV_{max}) will be used to determine the tumor lesions, defined as focal areas of abnormal uptake showing a higher SUV_{max} than surrounding tissue.

Identification of the time points post-injection with the highest observed number of lesions and the highest SUV_{max} , SUV_{mean} values and the tumor to background ratios for each SUV will be determined. The later will be conducted separately for each imaging time point (20-30 minutes, 1, 2, 3-4 h) post-injection through qualitative visual analysis of total number of lesions identified by PET, and semi-quantitative analysis by means of SUV_{max} and SUV_{mean} values and time point will be conducted.

Lesions suggestive of PCa will be counted and analyzed for radioactive uptake (expressed as SUV_{mean} and SUV_{max}) and localization. Any PCa lesion will be counted and analyzed. Tumor contrast will be measured by dividing the SUV_{mean} of tumor lesions by the SUV_{mean} of the background (e.g. gluteal musculature) and by dividing the SUV_{max} of tumor lesions by the SUV_{mean} of the SUV_{mean} of the background.

6.5.4.2. Biodistribution and Dosimetry Phase 1 Portion of the Study

Patients enrolled in the biodistribution and dosimetry set will undergo for a series of static whole-body PET/CT images at 20-30 minutes and at 1, 2 and 3-4h to determine absorbed doses to normal organs and to target tumor lesions. A low dose non-contrast-enhanced CT will be performed at 20-30 minutes, 1, 2, and 3-4 hours post injection. Immediately after CT scanning, PET scan will be performed from vertex to mid thighs in 3D (3-dimensional acquisition) mode at 20-30 minutes, 1, 2, and 3-4 hours imaging. The emission data will be corrected for dead-time, scatter, and decay, and resulting voxels were stored in units of Bq/mL. Reconstruction will be conducted with an ordered subset expectation maximization algorithm. Attenuation correction will be performed using low-dose non-enhanced CT data acquired at each time point.

Regions of Interest (ROIs)/ volume of interests (VOIs) will be drawn on the static whole-body PET images over the critical organs and tumor lesions to generate time-activity curves, and assess the time integrated activity coefficients (TIAC) (35). Up to 10 lesions which have the highest tumor to background ratio will be selected for dosimetry analysis for each patient.

Dosimetry calculations will be issued from the analyses of organs receiving the highest dose, identified visually. ROIs/VOIs will be placed over these organs to determine relative radiotracer uptake calculated as a percentage of the activity (%IA).

Tissue activity curves will be generated and fitted to mono- and bi-exponential curves to yield TIAC values. To assess pharmacokinetics and red marrow dosimetry, serial venous blood sampling withdrawn at immediately prior to IP administration, 5, 10, 20, 40 minutes, as well as immediately after, 1, 2, 4 and 6 hours post IP administration will be analyzed. Urine samples pre-injection, approximately 0-20 minutes after IP administration, 0 to 1 hour, 1 to 2 hours, 2 to 4 hours, and 4 to 6 hours post-injection will be collected to complete biodistribution and dosimetry assessments. The absorbed doses (μ Gy/MBq) for critical organs will be evaluated, as well as the effective dose (μ Sv/MBq).

6.5.4.3. Whole Body PET/CT Imaging for Phase 2 Portion of the Study

Preliminary data analysis from the Phase 1 portion of the study will provide sufficient dosimetry data, therefore all Phase 2 patients will have PET/CT imaging reduced to up to 2 whole body

scans within the optimal time frame, to confirm the high tumor to background ratio, and agreement compared to standard conventional method.

⁶⁸Ga PSMA-R2 PET/CT imaging will be performed using a standard integrated PET/CT system. Patients will be placed on the scanner table to allow a vertex to mid-thigh low-dose CT scan without contrast (used for anatomic localization and attenuation correction), followed immediately by emission imaging after ⁶⁸Ga-PSMA-R2 injection. A non-contrast-enhanced CT will be performed using routine investigational site imaging parameters. Immediately after CT scanning, PET scan will be performed from vertex to mid thighs in 3D (3-dimensional acquisition) mode. The scan duration will be 3 min for each bed position. The emission data will be corrected for dead-time, scatter, and decay, and resulting voxels were stored in units of Bq/mL. Attenuation correction will be performed using low-dose non-enhanced CT data acquired at each time point.

6.5.5. Other Safety Assessments

Results of the ECGs, and vital sign assessment will be evaluated by the Investigator for evidence of immediate safety concerns or for changes in values that indicate a potential danger for the patient to continue in the study. The Investigator should contact the medical monitor from Sponsor or designee (e.g. CRO) with questions regarding vital sign values.

6.5.5.1. Standard 12-Lead ECG

ECGs will be recorded at the screening visit and at Day 1 (after the administration of the IP) to measure the different ECG intervals (RR, PR, QRS, and a more extended QT evaluation according to ICH E14, and heart rate, HR). A single ECG will be taken supine, after 5 minutes rest, and not immediately after a meal. The parameters will be measured as a mean value of minimally 3 beats. The Investigator will note in the electronic CRF (eCRF) whether the ECG is normal or abnormal, as well as the clinical relevance of abnormal ECGs. Clinically relevant abnormalities will be recorded on the AE page of the eCRF.

6.5.6. Concomitant Medications and Other Restrictions

Any concomitant medication deemed necessary for the welfare of the patient during the study may be given at the discretion of the Investigator. However, it is the responsibility of the Investigator to ensure that details regarding the medication are recorded in full in the case report form, including any changes that have occurred during the study.

6.6. Reasons for Withdrawal

A patient may withdraw from the study at any time for any reason (see section 6.7).

The Investigator may discontinue the patient from the study if he experiences a serious or intolerable adverse event(s) or discontinue from study if the patient is in violation of the protocol.

Protocol can be terminated by the sponsor prematurely.

If a patient is discontinued due to an AE, the event will be followed until it is resolved.

6.7. Handling of Withdrawals

When a patient withdraws from the study, the reason(s) for withdrawal must be recorded by the Investigator in the patient's source document and the relevant page of the eCRF. For patients who remain in the study but fail to return for final assessments, every effort should be made to collect the information specified in the protocol.

It is vital to obtain follow-up data for any patient withdrawn as consequence of an AE. Every patient who discontinues prematurely must be contacted 15 Days (\pm 3 Days) after discontinuation to obtain adverse event information.

6.8. Sponsor's Termination of Study

The Sponsor reserves the right to discontinue the study at any time for clinical or administrative reasons. In that event, the Sponsor will immediately notify and instruct investigational sites, who in turn must promptly notify their patients and respective Institutional Review Board / Ethics Committee (IRB/EC) and or regulatory authorities.

6.9. Close-out of a Site

The sponsor and the investigator have the right to close-out a site prematurely.

6.9.1. Investigator's Decision

The investigator must notify the sponsor of a desire to close-out a site in writing, providing at least 30 days' notice. The final decision should be made through mutual agreement with the sponsor. Both parties will arrange the close-out procedures after review and consultation.

6.9.2. Sponsor's Decision

The sponsor will notify the investigator(s) of a decision to close-out a study site in writing. Reasons may include the following, among others:

- The investigator has received all items and information necessary to perform the study, but has not enrolled any patient within a reasonable period of time
- The investigator has violated any fundamental obligation in the study agreement, including but not limited to, breach of this protocol (and any applicable amendments), breach of the applicable laws and regulations, or breach of any applicable ICH guidelines
- The total number of patients required for the study are enrolled earlier than expected

In all cases, the appropriate IRB and Health Authorities must be informed according to applicable regulatory requirements, and adequate consideration must be given to the protection of the patients' interests.

6.10. Replacement Policy

Patients who discontinued for any reason during the study will not be replaced.

7. SAFETY DEFINITIONS, REPORTING, AND MONITORING

7.1. Adverse Events and Serious Adverse Events

The safety of the radiolabeled imaging final product ⁶⁸Ga-PSMA-R2 will be assessed through recording, reporting and analyzing medical conditions, infections, vital signs (temperature, blood pressure, heart rate, and respiratory rate), ECGs, and safety laboratory tests (blood chemistry, hematology, urinalysis).

Adverse events encountered from the time of ICF signature through the follow-up period (until Day 28 after administration of ⁶⁸Ga-PSMA-R2) will be recorded by the Investigator on the appropriate AE pages of the eCRF as defined in the following sections. Adverse events will be recorded using the Toxicity Grading Scale for Healthy Adult and Adolescent Volunteers Enrolled in Preventive Vaccine Clinical Trials (Section 11.2).

Only adverse events with start date on or after the IP administration date will be considered treatment emergent.

After the follow-up period, the Investigator must report to the Sponsor only SAEs possibly related to ⁶⁸Ga-PSMA-R2 or to the study procedures (see SAE definition in Section 7.6.3).

7.1.1. Adverse Events

An AE is defined as any untoward medical occurrence in the form of signs, symptoms, abnormal laboratory findings, or diseases that emerges or worsens relative to baseline during a clinical study with an investigational product, regardless of causal relationship and even if no investigational product has been administered.

In this study, the term "investigational product" refers to the radiolabeled imaging final product ⁶⁸Ga-PSMA-R2.

Unchanged/stable pre-existing, chronic medical conditions present at baseline, or those medical conditions related to the underlying disease should not be recorded on AE pages of the eCRF. However, in case of worsening of a pre-existing condition, this should be considered and reported as AEs.

- Relationship to IP,
 - based on temporal association: temporal relationship between administration of the IP and AEs occurrence is compatible,
 - based on AEs presentation and IP characteristics
 - If no alternative explanations (patient's medical history, patient's concomitant treatment, circumstance of AEs occurrence) are identified

- Not related to IP:
 - In case an alternative explanation regarding the AEs occurrence had been identified.

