1.1. Prostate Specific Membrane Antigen

Prostate Specific Membrane Antigen (PSMA) is a type II integral membrane glycoprotein identified on human prostatic carcinoma cell lines. The PSMA protein has a unique 3-part structure consisting in a 19-amino-acid internal portion, a 24-amino-acid transmembrane portion, and a 707-amino-acid external portion. The PSMA gene is located on the short arm of chromosome 11 in a region that is not commonly deleted in prostate cancer. PSMA triggers a signal that allows internalization of the protein on the cell surface into an endosomal compartment. This characteristic seems to be useful for diagnostic and therapeutic (theragnostic) approach in which PSMA could be used as an antigenic target or as a specific docking-station for tailored small molecules [11].

Increased PSMA expression has been detected most notably in prostate cancer; though, it was also detected in the peritumoral and endotumoral capillaries of a variety of malignancies including renal cell carcinomas, transitional cell carcinomas, and colon carcinomas [12]. Nearly all adenocarcinomas of the prostate demonstrate PSMA expression in most primary and metastatic lesions [13-14]. Immuno-histochemical studies have shown that PSMA expression increases in cases of de-differentiated, metastatic, or hormone-refractory disease [15] and its expression level is a significant prognosticator for disease outcome [16]. Since internalization occurs much easily after binding of small-molecule ligands to PSMA, these molecules may be the ideal candidates for peptide-radio-ligand therapy [17].

In addition to the promising emerging data on the use of PSMA-radioligands for the treatment of mPCa [18-20], PSMA is also expressed in normal tissues with relatively high density to potentially induce off-target effects, as in the red bone marrow, the salivary and lacrimal glands [21], or the kidneys [22]. The unwanted radio-ligand uptake can reach elevated absorbed doses in normal tissues [23-24] due to the variable tissue-binding site density and blood flow perfusion rate, which may lead to toxic effects.

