7.2. Abnormal Laboratory Findings and Other Objective Measurements

All clinically relevant abnormal laboratory findings must be captured and reported as AEs. Abnormal laboratory findings and other objective measurements that meet the criteria for SAE, result in discontinuation of the Investigational Product, or require medical intervention, should be captured and reported on the SAE/AE pages of the eCRF.

If reporting an abnormal laboratory finding on the AE pages of the eCRF, a clinical description or diagnosis should be recorded rather than the abnormal value itself, if this is available (for example "anemia" rather than "decreased red blood cell count" or "hemoglobin = 10.5 g/dL").

In the event of unexplained clinically abnormal laboratory values, the tests should be repeated immediately and followed up until returns to normal range and/or an adequate explanation of the abnormality is found. If a clear explanation is established, this must be recorded on the eCRF.

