7.7. Reporting Period

Adverse Events are collected on an ongoing basis from signing of Informed Consent until the last follow up visit.

All SAEs, including deaths, independently of causality, that occur from informed consent until the last scheduled follow-up visit will be recorded on an SAE form, in addition to the eCRF data entry. After the last follow-up visit, the Investigator must report to the Sponsor only SAEs possibly related to ⁶⁸Ga-PSMA-R2 or to the study procedures.

All SAEs must be followed-up by the Investigator until resolution or stabilization, and follow-up information must be reported to the Sponsor according to the reporting procedure.

All pregnancy cases occurring one week after IP administration and until the last follow-up (Day 28) will be reported according to the SAE reporting procedures. All pregnancy reports will be followed-up until delivery.

A last batch of queries will be sent after Last Patient Last Visit for all AEs with ongoing/unknown outcomes. After the last batch of queries with all collected data have been fully processed, eCRFs and database will no longer be updated. Only SAEs and medically relevant ongoing/unknown outcome AEs will be followed-up until resolution or stabilization. Beyond this defined reporting period, any new unsolicited serious AE spontaneously reported to CRO/Sponsor by the Investigator would however be collected and processed by pharmacovigilance.

Any patient who received a partial or full dose of the investigational product and who withdraws prematurely or is withdrawn by the Investigator from the trial, should have a follow-up safety visit 28 (\pm 3) Days after the investigational product administration.

If a patient is documented as lost-to follow-up or consent withdrawal, ongoing/unknown outcome AEs will not be followed-up.

For screen failure patients, new AEs and updates must be recorded in eCRFs until the date the patient was determined to be a screen failure. Beyond that date, only SAEs possibly related to the investigational product or to the study procedures will be reported to the CRO/Sponsor.

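### Protocol 7.1.1 keeps conditions related to the underlying disease off the AE page, against its own AE definition, so new non-serious events attributed to the cancer can go unrecorded

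*Protocol*

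**What the plan says.** Protocol 7.1.1 takes an AE to be any untoward medical occurrence "that emerges or worsens relative to baseline during a clinical study with an investigational product, regardless of causal relationship". Later in the section, one sentence names two classes that stay off the AE page. The first is chronic conditions that were present at baseline and are unchanged. The second is added, after an *or*, as "those medical conditions related to the underlying disease should not be recorded on AE pages of the eCRF". The next sentence gives the only exception: "However, in case of worsening of a pre-existing condition, this should be considered and reported as AEs".

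Other sections bear on the same question:
- Protocol 7.2: "All clinically relevant abnormal laboratory findings must be captured and reported as AEs".
- Protocol 7.3 exempts only conditions present at screening that do not get worse.
- Protocol 7.5 sends worsening of symptoms to the AE page.
- Protocol 7.6.2 asks each AE report for causality and any other causal factors.
- Protocol 7.6.3 requires every SAE to be reported whatever its relationship to the product, and gives underlying disease as an example of a cause to be stated.
- Protocol 7.7 requires an SAE form, in addition to eCRF entry, for "All SAEs, including deaths, independently of causality".

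Incidence and severity of AEs and SAEs is a primary endpoint (Protocol 2.2.1). The SAP identifies serious events (14.1.3) and fatal events (14.1.4) from the AE page of the eCRF.

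**The concern.** The definition covers a new event whatever its cause, yet the exclusion removes a group of events because of their cause. An investigator who knows that the patient has been injected must decide whether a new complaint belongs to the cancer. Under the literal rule, a yes means that nothing is entered, so nobody can review that decision later.

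The study is single-arm and its primary purpose is a description of AE incidence. Omission under this rule can only lower the count. Sites may also read the clause differently, so recorded incidence could depend partly on where a patient was enrolled. Attribution to the cancer is plausibly more frequent in mPCa patients, who have documented metastases, than in PCa-BR patients, whose CT/MRI or bone scan must show no local recurrence or metastasis (Protocol 4.1). The SAP tabulates these groups separately (6.1).

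**Working it through.** This is mainly a comparison of texts. The plan gives no figure on the point to reproduce. The one computed interval in Protocol 8.1 concerns imaging agreement and plays no part here.

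**Step 1. Scope of the exclusion.** The qualifiers (unchanged, stable, present at baseline) attach to the first class. The second class is joined by an *or* and carries none of them. The exception restores worsening of a pre-existing condition and does not mention a new one.

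**Step 2. Set against the other sections.**

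| Event attributed to prostate cancer | 7.1.1 definition | 7.1.1 exclusion, read literally | Other sections |
|---|---|---|---|
| Worsening of a condition present at baseline | AE | Restored by the exception | 7.3 and 7.5: record |
| New laboratory abnormality, clinically relevant | AE | Kept off the AE page | 7.2: report as AE; laboratory data also tabulated separately (SAP 14.2) |
| New serious event | AE | Kept off the AE page | 7.6.3 and 7.7: report and record |
| New non-serious clinical event (e.g. bone pain, urinary retention) | AE | Kept off the AE page | 7.3 does not exempt it; no section specifically requires it |

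The last row is the unprotected one. Only the general definition, and the narrow exemption in 7.3, stand against the exclusion there.

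**Step 3. Can the analysis recover an event that was not entered?** The worst-case rules for missing severity and relationship (SAP 14.1.1.1 to 14.1.1.3) and the partial-date rules (SAP Appendix 2) act on events already in the database. The listings of TEAEs and non-TEAEs (SAP 14.1) have the same source. A serious event that reached the SAE form but not the AE page would be missing from the SAP 14.1.3 and 14.1.4 tables.

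**Step 4. Size per patient.** The inputs are the planned numbers: 30 overall (Protocol 8.1) and 12 in the mPCa group (Protocol 3.1).
- Overall: 1/30 = 3.3 percentage points.
- mPCa: 1/12 = 8.3 percentage points.

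For the any-event row, these apply only to a patient with no other recorded TEAE. For a single preferred-term row, they apply to a patient whose only event of that term is omitted.

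**Step 5. Illustration with assumed rates.** Neither rate below is in the documents. Let r be the true per-patient rate of some event, and q the share attributed to the cancer and left off. The chance that at least one of 30 patients shows it in the data is 1 − (1 − r(1 − q))^30.

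| r | q = 0 | q = 25% | q = 50% | q = 75% |
|---|---|---|---|---|
| 5% | 78.5% | 68.2% | 53.2% | 31.4% |
| 10% | 95.8% | 90.4% | 78.5% | 53.2% |

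This shows what under-recording would do to a study of this size. It is not an estimate of how much will occur.

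**The case against.** The best defence is that the protocol plainly expects disease-caused events to be recorded. Section 7.6.3 asks for underlying disease as a possible SAE cause. Section 7.6.2 asks for other causal factors. Section 7.1.1 itself classes an event as not related when another explanation exists, which presupposes that the event was entered. A charitable reader could carry the word stable over to the second class, or treat any new cancer manifestation as worsening of a cancer that every patient already has. These readings are possible, but the text states neither. The sections cited in the defence also deepen the conflict with the exclusion.

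The defence does limit the harm, and four stronger readings should be resisted.
- A reader might infer that the loss falls on marrow and kidney, because Protocol 1.1 says that PSMA expression in normal tissue could "potentially induce off-target effects, as in the red bone marrow, the salivary and lacrimal glands" and adds the kidneys. The documents do not support this. Anemia, creatinine rise and hematuria are picked up by the laboratory tests at Screening, Day 1, Day 7 and Day 28 (6.5.3). Laboratory change is a separate primary endpoint, and SAP 14.2 tabulates it without using the AE page.
- A reader might infer that 7.2 and 7.7 require every event to be recorded regardless of cause. The causality wording in 7.7 covers SAEs only. Section 7.2 covers laboratory and other objective findings and does not mention causality.
- A reader might infer that serious events are lost. Sections 7.6.3 and 7.7 require them; they leave the AE tables only if a site applies 7.1.1 over those sections.
- A reader might put a number on the patients affected, say 10% to 30% of 30, or 3 to 9. No document gives such a rate. One rate for all 30 also ignores that about 18 (6 + 12) are PCa-BR patients with negative conventional imaging.

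It is also fair to say that the phrase "regardless of causal relationship and even if no investigational product has been administered" most naturally refers to the product. The conflict does not depend on it, because any untoward occurrence that emerges already includes one caused by the disease.

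**Conclusion.** The point holds in limited form. The exclusion contradicts the protocol's own AE definition and is out of line with 7.3 and 7.6.3. A site that follows it literally can leave a new, non-serious, cancer-attributed clinical event out of the AE component of the primary endpoint, with no route to recovery in the SAP. The effect runs in one direction and may vary by site and by population.

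The conclusion rests on a literal reading of the clause, so events can be lost; the documents do not show that they will be. The laboratory, vital-sign and ECG components are unaffected. The total loss cannot be estimated. The per-patient figures of 3.3 and 8.3 points assume that planned enrollment is reached. This should be corrected, but it does not undermine the safety assessment as a whole.

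**What to change.** In the clause "or those medical conditions related to the underlying disease should not be recorded on AE pages of the eCRF", delete everything up to and including the word disease, so that the sentence exempts only stable conditions present at baseline. State in 7.1.1 that every condition new or worse after consent goes on the AE page, whatever its presumed cause. Enter attribution to prostate cancer as the alternative cause, which 7.6.2 already accommodates. Put the same instruction in the eCRF completion guideline so that sites act alike.

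If the sponsor wants a view without disease-attributed events, the SAP can add it as a supplementary TEAE table and keep the all-event table as the primary display. If patients have already been followed up when the change is made, sites would need to be asked about events left off, because the analysis cannot restore them.

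The cost is a one-sentence amendment and a guideline update. The downside is small: more AE entries and a slightly higher reported AE incidence. Nothing changes in how patients are managed.
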